### 19.8.4. OBSERVATIONAL ENDPOINTS

All observational endpoints will be summarized descriptively.

### 19.9. SUBGROUP ANALYSIS

The primary safety and efficacy endpoints will be re-analyzed stratifying by gender and by US versus OUS. Point estimates and 95% confidence intervals will be displayed for each endpoint. No formal testing will be done since the reduced sample sizes would result in underpowered tests.

#### 19.10. SITE POOLING ANALYSIS

For both the primary safety endpoint and the primary efficacy endpoint, a pooling analysis will be completed demonstrating that the information on the primary endpoints can be pooled across site. For each endpoint, the site specific estimate of the endpoint will be calculated. These site specific rates will then be compared using a standard Pearson chi-square statistic. A p-value greater than 0.15 will indicate poolability of site information. Low enrolling sites (enrollment  $\leq 5$ ) will be pooled into an “other site” category for the purposes of this analysis. If differences between sites exist at the  $\alpha=0.15$  level, summary statistics will be presented for each site and any differences by study site will be discussed in the study report. In this case, a meta-analytic modeling approach will be used to combine the estimates across sites using the random effects estimate based on the inverse variance to account for the heterogeneity of sites. Specifically, each of the binary primary endpoints will be modeled as a function of the random effect of site and the estimates and resulting confidence intervals used to compare the estimate to the performance goal. The DerSimonian-Liard estimator of the variance with inverse variance weights will be used to adjust for the random effect of site in the final analysis. Additionally, a sensitivity analysis of the primary outcomes will be performed by excluding outlying sites one at a time until a statistically significant difference between sites (at  $\alpha=0.15$ ) no longer exists. Then, the pooled results for the remaining sites will be used for the sensitivity analysis.

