and a one-sided Type I error rate of 2.5%, a sample size of 171 subjects provides 90% power to demonstrate that the observed 30-day MALE+POD rate is below the performance goal of 12%.

Since the required sample size for the primary efficacy endpoint (186), is larger than the required sample size for the primary safety endpoint (171), an effective sample size of 186 subjects meeting the ITT definition will be assumed. Assuming approximately 20% loss to follow-up, total enrollment will be  $186/0.80$  or 232 subjects.

The secondary endpoint of primary patency of the tacked segment of the treated lesion at 6 months will also be formally tested against a performance goal of 64%. The performance goal of 64% was chosen as a result of a meta-analysis combining 13 papers that reported 6-month patency for standard PTA or from which the 6-month patency rate could be derived. These papers covered several patient populations, however all these populations are target populations for use of the Tack. A meta-analysis was performed on the results reported in these papers and the random effects estimate of 6-month patency was 63.5%. Therefore, 64% was chosen as the performance goal. Assuming an observed 6-month patency rate of 81% and a one-sided Type I error rate of 2.5%, the effective sample size given above for the primary efficacy endpoint of 175 would provide greater than 90% power to detect the difference between an observed 6-month patency of 81% and the performance goal of 64%.

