#### 19.8. STATISTICAL ANALYSIS

##### 19.8.1. PRIMARY SAFETY

The primary safety endpoint of MALE+POD at 30 days will be analyzed by constructing a one-sided upper 97.5% confidence interval using the exact binomial distribution. This upper bound will be compared to the performance goal of 12%. The hypotheses being tested are:

$$H_0 : P_{MALE+POD} \geq 12\%$$

$$H_a : P_{MALE+POD} < 12\%$$

where  $P_{MALE+POD}$  is the proportion of subjects experiencing a MALE+POD event within 30 days of the procedure. All subjects that meet the ITT definition are included in this analysis.

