##### 19.8.2. PRIMARY EFFICACY

The primary efficacy endpoint of freedom from MALE at 6 months plus POD at 30 days will be analyzed using a one-sided, single group, Z-test comparing the observed proportion of subjects free of MALE and POD to the performance goal of 74%. The hypotheses are:

$$H_0 : P_{MALE\_6+POD} \leq 74\%$$

$$H_a : P_{MALE\_6+POD} > 74\%$$

where  $P_{\text{MALE}_{6+\text{POD}}}$  is the proportion of subjects free of MALE at 6 months + POD at 30 days. The p-value associated with the standard Z-test will be provided along with a one-sided 97.5% lower confidence bound on the point estimate observed. All subjects that meet the ITT definition are included in this analysis.

The Z-test that will be used for analysis is the continuity corrected Z under the estimated  $P_{\text{MALE}_{6+\text{POD}}}$ . That is:

$$Z = \frac{\hat{p} - P_0 + c}{\sqrt{\hat{p}(1 - \hat{p})/n}},$$

where  $\hat{p}$  is the estimate of  $P_{\text{MALE}_{6+\text{POD}}}$ ,  $P_0$  is the performance goal of 74% under the null hypothesis, and

$$c = \begin{cases} -\frac{1}{2n} & \text{if } \hat{p} > P_0 \\ \frac{1}{2n} & \text{if } \hat{p} < P_0 \\ 0 & \text{if } |\hat{p} - P_0| < \frac{1}{2n}. \end{cases}$$

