#### 19.11. HANDLING OF MISSING DATA

For the primary analysis, only complete data will be used. Data will be considered “complete” if the subject had the event of interest at or prior to the time point for analysis and/or if the subject’s status is known at any time beyond the analysis window. Subjects without sufficient follow-up based on the lower end of the visit window will be excluded from the analysis (that is, subjects must have at least 28 days of follow-up for the 30 day endpoints, 6 months minus 30 days for the 6 month endpoints and 12 months minus 30 days for endpoints defined at 1 year). Thus, subjects without events but whom are known to be event free at a later visit will have their data imputed backward but not forward for the primary analysis.

As a sensitivity analysis, missing values for the primary endpoints will be replaced by regression imputations based on a multivariate logistic regression analysis of completed cases (those that have follow-up at the required time point or experienced the endpoint in question prior to final follow-up visit). Covariates to consider for inclusion in the logistic regression include but are not limited to: age, sex, history of hypertension, diabetes, previous peripheral vascular intervention, BMI, dissection location (mid popliteal (P2), distal popliteal (P3), tibioperoneal trunk, peroneal, anterior tibial, or posterior tibial), and baseline Rutherford class. Backward selection will be used to identify predictors. In the event there are no significant predictors in the logistic regression model at  $\alpha=0.1$ , a “hot deck” method will be employed where a random selection of the outcome from a group of completed cases with similar baseline characteristics will be used as the imputed value using simple random sampling with replacement. The baseline characteristics to be used for the hot deck method will include but are not limited to age ( $\neq$  median), sex, dissection location (mid popliteal (P2), distal popliteal (P3), tibioperoneal trunk, peroneal, anterior tibial, or posterior tibial), use of statin medication, current smoker status and baseline Rutherford class.

With either method of imputation, five complete datasets will be constructed. Each dataset will be analyzed separately and then combined in an overall analysis across the five complete datasets.

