#### 19.12. STUDY SUCCESS DEFINITION

The trial will be considered a success if both the primary safety and primary efficacy endpoints are met.

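### When sites differ at p≤0.15, the DerSimonian-Laird comparison in section 19.10 cannot be run with zero-event sites as written, and on its natural raw-rate reading it can raise the safety false-pass rate

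*Combined protocol and SAP*

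**What the plan says.** Section 19.10 (Site Pooling Analysis) compares site-specific rates with a Pearson chi-square for each primary endpoint. Sites with five or fewer subjects are first merged into one category. The rule is that "A p-value greater than 0.15 will indicate poolability of site information".

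Otherwise the site estimates are combined by an inverse-variance random-effects method, with "the estimates and resulting confidence intervals used to compare the estimate to the performance goal". The section then says that the "DerSimonian-Liard estimator of the variance with inverse variance weights will be used to adjust for the random effect of site in the final analysis". It also requires per-site summaries and a sensitivity analysis that drops outlying sites.

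Where sites are poolable, section 19.8.1 tests safety with an exact binomial upper 97.5% bound against 12%. Section 19.8.2 tests efficacy with a continuity-corrected Z-test against 74%. Section 19.12 adds: "The trial will be considered a success if both the primary safety and primary efficacy endpoints are met".

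Nothing in sections 19.8 to 19.13 says what to do with a site that has no events, or states the scale or back-transformation for the pooled estimate.

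**The concern.** An inverse-variance weight is one over the estimated variance. For a site with no events the raw-scale variance is zero and the weight infinite; on the logit scale the site estimate itself is undefined. Someone must add a rule, and the plan supplies none.

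There is a second difficulty even after a patch. On the raw scale the variance r(1−r)/n shrinks with the observed rate r. Sites that happen to have few events therefore get the most weight, and the pooled event rate is pulled down. For a safety endpoint that must fall below 12%, this favours passing.

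The study is single-arm and unblinded and both primary endpoints must be met. An analyst who settles the scale and patch after seeing site counts could know which choice passes.

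**Working it through.** **The plan's own figure.** Section 19.6 gives 171 subjects for safety (12% goal, 5% assumed, one-sided 2.5%). Exact binomial at n=171: pass with 12 or fewer events, false-pass 2.36%, power 91.1%. The stated 90% is reproduced. At full enrolment, n=230 passes with ≤17 events (false-pass 1.57%, power 95.9%) and n=232 with ≤18 (2.46%, 97.5%).

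**How often a site has no event at 5%.** 0.95^6 = 0.735; 0.95^10 = 0.599; 0.95^46 = 0.094. Even with five sites at the 46-subject cap, at least one has no event in 1 − (1 − 0.094)^5 = 39% of trials. With many small sites it is close to 100%. Merging sites of five or fewer does not remove the problem.

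**Worked example.** Five sites of 46 with 6, 3, 2, 1 and 0 events: 12/230 = 5.2%; chi-square 9.32 on 4 df, p=0.054, so the random-effects route applies. Add 0.5 event and 0.5 non-event to the zero site only. With w = 1/variance, Q = Σw(y − ȳ)², C = Σw − Σw²/Σw and τ² = (Q − 4)/C:

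- Raw scale. Rates 13.04, 6.52, 4.35, 2.17, 1.06%. Variances 0.002466, 0.001325, 0.000904, 0.000462, 0.000224. Q = 6.994, C = 5907, τ² = 2.994/5907 = 0.000507. Final weights 8.4, 13.7, 17.8, 25.9, 34.3%. Estimate 3.69%, SE 1.583%. Upper bound 3.69 + 1.96×1.583 = **6.8%: pass**.
- Logit scale. Logits −1.897, −2.663, −3.091, −3.807, −4.533. Variances 0.192, 0.357, 0.523, 1.022, 2.022. Q = 6.307, C = 7.906, τ² = 2.307/7.906 = 0.292. Final weights 34.3, 25.6, 20.4, 12.6, 7.2%. Estimate −2.766 (5.9%), SE 0.407. Upper bound −2.766 + 1.96×0.407 = −1.968, which is **12.3%: fail**.
- For reference: exact bound on the pooled data 8.9%; Freeman-Tukey with simple back-transformation 10.4%.

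The raw estimate (3.7%) lies below the crude rate (5.2%) because the zero-event site takes about a third of the weight and the six-event site about a twelfth.

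**Frequency.** Simulation of the whole safety procedure: the chi-square at 0.15, then the DerSimonian-Laird bound (1.96 SE) or the exact test; identical sites; 40,000 trials per setting; 230 to 232 subjects. The six layouts are assumptions, ranging from five sites of 46 to about 57 sites, most of them merged.

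- The switch fires in about 13% to 17% of trials.
- False-pass at a true 12%: exact 1.6% to 2.5%; raw with 0.5 in zero cells about 2.4% to 8%; raw with 0.5 at all sites 1.8% to 4.0%; logit 1.4% to 2.2%; Freeman-Tukey, simple back-transformation, 1.5% to 2.4%.
- Power at a true 5%: exact 96% to 98%; logit about 82% to 90%; Freeman-Tukey, simple, 94% to 97%.
- Raw against logit, both with 0.5 in zero cells, at a true 5%: opposite verdicts in 45% to 95% of triggered trials. Multiplied by the trigger frequency layout by layout, this is about 6.5% to 13.5% of all trials.
- Raw scale held fixed and only the patch changed: opposite verdicts in under 1% of all trials at a true 5%, but in about 4% to 29% of triggered trials at a true 12%.

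**Efficacy.** Section 19.6 states that "an effective sample size of 186 subjects meeting the ITT definition will be assumed". With layouts thinned to 186 evaluable subjects, power is 93% to 94% for the Z-test and 81% to 88% for logit. False-pass is 3.1% to 3.4% for the Z-test and 3.0% to 5.7% for raw with 0.5 in zero cells.

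**The case against.** The strongest reply is that section 19.10 is not silent on scale. It speaks of rates calculated per site and then combined, and the goals are proportions, so the raw scale is the natural reading and needs no back-transformation. That stands, and a reader should not infer that the plan gives no indication of scale. One sentence, which models each endpoint as a function of a random site effect, leaves some ambiguity. The natural reading does not rescue the rule, however: it is the one whose variance is zero at zero events and whose patched version has the raised false-pass rate.

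A reader might also infer that the missing zero-event rule by itself produces the 45% to 95% disagreement. It does not. That figure is a scale effect, conditional on the trigger. In the example the patch alone changes nothing: 0.5 at all sites moves the raw bound from 6.8% to 8.3% (still a pass) and the logit bound from 12.3% to 13.0% (still a fail). The patch matters mainly near the 12% boundary.

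A third tempting reading is that the plan leaves open which analysis decides success. Section 19.10 says that this one is the final analysis, so missing cross-references are editorial. The one-sided 97.5% level can likewise be taken from sections 19.8.1 and 19.8.2.

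It is also fair that the route is contingent, that per-site summaries and a site-exclusion analysis accompany it, that site sizes are assumed, and that five sites at the cap is close to the fewest the plan allows when up to 60 are planned. These points limit the size of the problem; they do not supply the missing rule.

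**Conclusion.** The point holds in two parts. First, the final analysis prescribed for p≤0.15 cannot be computed when a site has no events, which is expected at the planned safety rate. On the raw scale with 0.5 in zero cells, it raises safety false-pass from 1.6%–2.5% to about 2.4%–8%. Second, because the scale is only implied, a choice made after the data are seen could decide the safety result in about 6.5% to 13.5% of trials at a true 5%.

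The harms differ by version: raw weighting raises false-pass, whereas logit loses power. The documents do not support a claim that every DerSimonian-Laird version inflates error.

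All frequencies rest on assumed site layouts with no true site differences. The zero-event probabilities and the worked example's arithmetic do not depend on the simulation. This should be fixed; it is contingent, but it can reverse a primary endpoint.

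**What to change.** In section 19.10, before data are seen, replace raw inverse-variance weighting with one prespecified estimator that is defined at zero events. State its scale, its back-transformation and its one-sided 97.5% bound. Two options would serve, and neither is the only right choice:

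- a binomial-likelihood model with a random site effect;
- DerSimonian-Laird on the Freeman-Tukey double-arcsine scale, variance 1/(n+0.5), with the simple back-transformation sin²(t/2).

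Do not use raw-scale weights with 0.5 added only in zero cells. Cross-references in 19.8.1, 19.8.2 and 19.12 would help readers but are editorial.

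The cost is SAP wording, no new data, and some power. With identical sites the Freeman-Tukey option loses 0.4 to 3.4 points of safety power against the exact test, and 1.4 to 6.5 points of efficacy power against the Z-test at 186. A beta-binomial model has safety power of 85% to 96% and efficacy power of 84% to 92%.

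The loss grows if sites truly differ. At an assumed intraclass correlation of 0.03, Freeman-Tukey safety power is 77% to 94% (exact test 87% to 96%) and efficacy power 69% to 87% (Z-test 82% to 91%). Safety false-pass is then 3.7% to 7.6%, against 4.2% to 14.6% for the exact test: lower, but still above 2.5%. The SAP should state this downside.

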#### 19.6. SAMPLE SIZE

The sample size for the primary efficacy endpoint of freedom from MALE at 6 months plus POD at 30 days was calculated using a one-sided, single group, normal approximation test of a proportion (with continuity correction) against a performance goal. The performance goal for this endpoint is 74% developed based on the information reported in table VIIb and figure 2A of Conte (2009). From figure 2A, the estimated 6-month rate of freedom from MALE + POD in the infra-popliteal group is 80.5% with 95% confidence interval calculated to be (77%, 84%). Applying the recommended 3% margin to the lower bound of the confidence interval yields the 74% OPG. Assuming the observed freedom from MALE+POD is 84% and a one-sided Type I error rate of 0.025, a sample size of 186 subjects provides 90% power to detect this difference between observed freedom from MALE+POD and the performance goal of 74%.

The sample size for the primary safety endpoint of MALE+POD at 30 days was calculated using the exact binomial distribution. This is also a one-sided, single group test of a proportion against a performance goal. The performance goal for this endpoint was established at 12%. This performance goal was derived from the information reported in table VIIa of Conte (2009). In that table, MALE+POD was not reported, however MALE and 30-day death were reported separately. The sum of those two estimates (8.9%) was used for sample size calculation. Conte (2009) established performance goals for safety endpoints by constructing a 95% confidence interval and using the upper bound of that interval as the performance goal. With some algebraic manipulation, a similar 95% confidence interval was established for the 8.9% point estimate of 30day MALE+POD which resulted in an upper bound of 11.9%. Therefore 12% is used as the performance goal for this endpoint. Assuming an observed MALE+POD rate of 5%

 Joseph L. Mills, Sr, MD, [name], David G. Armstrong, DPM, MD, PhD, [name], [name], [name], MPH, and [name], on behalf of the Society for Vascular Surgery Lower Extremity Guidelines Committee, The Society for Vascular Surgery Lower Extremity Threatened Limb Classification System: Risk stratification based on Wound, Ischemia, and foot Infection (WIFI). J Vasc Surg. 2014; Volume 59, Issue 1, Pages 220–234.e2

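### The site sensitivity analysis in Section 19.10 deletes sites on their observed outcomes until heterogeneity disappears, which biases the sensitivity estimates (not the primary analyses) in the device's favour

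*Combined protocol and SAP*

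**What the plan says.** Section 19.10 (Site Pooling Analysis) compares site-specific rates of each primary endpoint with a Pearson chi-square: "A p-value greater than 0.15 will indicate poolability of site information". Sites that enrol five or fewer subjects "will be pooled into an “other site” category for the purposes of this analysis".

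If the sites differ, three things follow:

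- Results are summarised for each site, and site differences are discussed in the report.
- A random-effects analysis over all sites is compared with the performance goal. The DerSimonian-Laird "estimator of the variance with inverse variance weights will be used to adjust for the random effect of site in the final analysis".
- A further step, which the plan labels a sensitivity analysis and applies to both primary endpoints, removes sites in sequence. It proceeds by "excluding outlying sites one at a time until a statistically significant difference between sites" has gone, judged at the 0.15 level. The text ends: "Then, the pooled results for the remaining sites will be used for the sensitivity analysis".

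The plan does not define 'outlying'. It gives no limit on the number of exclusions, no rule for their order beyond one at a time, and no allowance for the selection.

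**The concern.** Sites are chosen for removal on the outcome being estimated, and removal stops once that outcome looks homogeneous. The rule reads as symmetric, but the data are not. With failure rates between 5% and 26%, a small site can lie far above the pooled failure rate and only a little below it. The rule therefore mainly trims failures.

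A sensitivity analysis of this kind will be read as showing whether the conclusion survives disagreement between sites. This one discards the sites that disagree and reports a rate that leans towards the device. In a single-arm, non-blinded study meant to support a premarket application (Section 16.3), an analysis cited for robustness should not lean that way. The tipping-point analysis in Section 19.11, by contrast, stresses the result towards failure.

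**Working it through.** **Inputs from the documents.**

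- Efficacy (Section 19.6): goal 74% (26% failures), alternative 84% (16% failures), N = 186, one-sided alpha 0.025, power 90%.
- Safety (Section 19.6): goal 12%, alternative 5%, N = 171, one-sided alpha 2.5%, power 90%.
- Enrolment (Section 7.1): up to 232 subjects at up to 60 sites, at most 46 per site.
- Site rule (Section 19.10): test at 0.15, sites of five or fewer subjects pooled.

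**Step 1: the plan's own figures.** The plan gives no operating characteristic for the deletion rule, so the sample sizes were checked first.

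- *Efficacy.* Without continuity correction, n = [(1.96·√(0.74·0.26) + 1.2816·√(0.84·0.16)) / 0.10]² = 176.8. With the correction, n = (176.8/4)·[1 + √(1 + 2/(176.8·0.10))]² = 186.6. Power at 186 is 0.899, so the stated 186 is reproduced.
- *Safety.* At n = 171 the exact upper 97.5% bound lies below 12% with 12 or fewer events. This gives alpha 0.0236 and power 0.911, consistent with the stated 90%.

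**Step 2: why the direction is built in.** A site with n subjects and x failures, against a pooled failure rate p, has Pearson residual (x − np)/√(np(1 − p)). With no failures this equals −√(np/(1 − p)).

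| Failure rate | Failure-free site | Small site with failures |
|---|---|---|
| 5% (safety alternative) | n = 46, the site cap: −√(46·0.05/0.95) = −1.56 | 2 of 8: (2 − 0.4)/√0.38 = +2.6 |
| 16% (efficacy alternative) | reaches −2 only at n = 21: −√(21·0.16/0.84) = −2.0 | 4 of 8: (4 − 1.28)/√1.075 = +2.6 |
| 26% (efficacy goal) | passes −2 at n = 12: −√(12·0.26/0.74) = −2.05 | 5 of 8: (5 − 2.08)/√1.539 = +2.35 |

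The asymmetry is strong at low failure rates and weaker at 26%.

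**Step 3: simulation of the rule with identical sites.** There were 3,000-8,000 trials per scenario, with N = 186 for efficacy and 232 for safety. Efficacy was retested with the plan's Z-test and safety with the exact bound. The documents do not fix two inputs, so both are assumptions:

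- *Site layout:* 10 equal, 20 equal, 20 tapering, 40 skewed or 60 skewed sites.
- *Meaning of 'outlying':* largest chi-square contribution, rate furthest from the pooled rate, or the deletion that most raises the p-value.

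| Result | Efficacy | Safety |
|---|---|---|
| Deleted sites above the pooled failure rate, all readings | 58-100% | 57-100% |
| Same, first two readings | 71-100% | 91-100% |
| Fall in mean failure rate, all readings | 0.4-2.5 points | 0.2-2.3 points |
| Same, first two readings | 1.3-2.5 points | 1.2-2.3 points |
| Pass rate in triggered trials, true rate at the goal | 2-5% → 8-16% | 1-3% → 6-17% |

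The rule was triggered in about 12.5-16% of trials and usually removed one or two sites. The mean failure rate fell in every scenario.

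**Step 4: comparator.** In triggered datasets, omitting each site category once with no stopping rule moved the mean failure rate by 0.00 to +0.08 points. It has almost no directional bias.

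**The case against.** The strongest objection concerns scope. A reader might infer that the rule biases the primary endpoints or the success decision. The documents do not support that. Sections 19.8.1 and 19.8.2 analyse all ITT subjects (subject to the completeness rule in 19.11). When sites differ, 19.10 makes the all-site random-effects estimate the one compared with the goal, and 19.12 rests success on the primary endpoints. Nothing lets the reduced-site result replace them, and it would appear beside per-site summaries. This objection stands in full. If the reduced data did decide every triggered trial, the false-pass rate over all trials would move from about 2.7-4.0% to 3.8-5.1% (efficacy) and from 2.1-2.7% to 3.0-4.8% (safety), but the plan does not use them so.

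A second tempting inference is that deleted sites are nearly always high-failure sites. That depends on how 'outlying' is read. Under the p-value reading the share drops to 57-94%, and in a minority of triggered trials the result moves against the device.

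A third is that deletion always makes a pass more likely. It does not. At the planning alternatives fewer subjects remain, and the pass rate can fall. In one efficacy layout, with the p-value reading and a large 'other site' group open to deletion, it fell from 0.935 to 0.797.

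It can also be said that defining 'outlying' would be enough. It would narrow the range of results, but selection on the outcome would remain: the mean shift favoured the device under each definition tried.

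**Conclusion.** The concern holds for the site sensitivity estimates of both primary endpoints. As written, the rule shifts them towards the device on average even when no site differs from any other, so it cannot serve as evidence of robustness. The size is modest: at most about 2.5 points on the failure rate, in the roughly one trial in seven where identical sites trigger the rule by chance. It matters most near the performance goal, where passes in triggered trials become several times as frequent.

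The direction of the mean shift was the same in every scenario. Its size rests on the assumed site layouts and the assumed meanings of 'outlying', and is therefore given as a range. The primary analyses, the all-site random-effects analysis and the definition of study success are not affected. The plan should be changed, but the point does not threaten the trial's main conclusion.

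**What to change.** Replace the sequential exclusion rule in Section 19.10 with a leave-one-site-out analysis. Recompute each primary endpoint with each site category omitted in turn, including the pooled small-site category. Report the full range and whether any single omission changes the conclusion against the performance goal, beside the all-site random-effects result.

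If the sponsor keeps the deletion analysis, the SAP should define 'outlying' and label the result descriptive. It should also require a report of which sites were removed and in which direction each lay, and the result should not be cited as support for robustness.

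The cost is SAP wording and a short program, with no new data or subjects. The sensitivity result may look slightly less favourable. Single omissions also do not show the joint effect of several aberrant sites; the per-site summaries and the random-effects estimate already planned partly cover that.
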